## **10.2.2.2** Extension Phase Analyses

Evaluation of the efficacy data will consist primarily of summary displays and data listings.

# 10.2.3 Analysis of Safety

Evaluation of safety will be performed on the Safety Set. Safety data that will be evaluated include AEs, clinical laboratory results, and vital signs. All AEs will be coded using MedDRA. Adverse events will be coded to system organ class and preferred term using MedDRA. AEs will be presented with and without regard to causality based on the Investigator's judgment. The frequency of overall toxicity, categorized CTCAE criteria Grades 1 through 5, will be described. Treatment-emergent AEs (TEAEs) will be summarized by presenting the incidence of AEs. Descriptive summary statistics (mean plus standard deviation, median, and range) of the laboratory parameters, vital signs, and changes from baseline will be evaluated.

## **10.2.4 Interim Analysis**

No formal interim analysis is planned for this study.

## 10.2.5 Hurdle and Sample Size Determination

To determine a clinically relevant efficacy hurdle, data from a 26-week open-label extension of eltrombopag study TRA108109 in adult Japanese patients with chronic ITP were used as a benchmark. This study evaluated the endpoint of cumulative number of weeks of platelet response ( $\geq 50 \times 10^9/L$ ) in a comparable population of patients who received eltrombopag for 26 weeks. The results were similar to those in avatrombopag overseas Study 302, with a reported mean of 11.2 weeks with 95% CI of 8.02 and 14.38 weeks.

The lower limit of the 95% CI of the cumulative number of weeks of platelet response, or 8.02, from study TRA108109 is set as the efficacy hurdle for the lower limit of the 95% CI in this study. Assuming a distribution of results (mean of 12.0 cumulative weeks and standard deviation of 8.75) similar to that observed in Study 302, a sample size of 19 subjects would be required to meet this primary efficacy endpoint hurdle.

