### **SAMPLE SIZE DETERMINATION:**

Assuming a distribution of results similar to that observed in the overseas Study 302, a sample size of 19 subjects is required to meet the primary efficacy endpoint hurdle of a lower limit of 95% CI  $\geq 8.02$  weeks of cumulative platelet response.

**SITES:** The study will be conducted at approximately 18 sites in Japan.

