### 4 STUDY DESCRIPTION

# 4.1 Summary of Study Design

This study is an open-label study of avatrombopag in Japanese men and women  $\ge 18$  years who have chronic ITP. Approximately 19 subjects who meet all the eligibility requirements will be enrolled. The Screening Visit and Day 1 Baseline Visit platelet counts will be averaged to obtain the baseline platelet count value. The 2 samples must be obtained  $\ge 48$  hours and  $\le 2$  weeks apart and the results must be available prior to enrollment. No single platelet count can be  $> 35 \times 10^9 / L$ . An additional screening platelet count is required if the second platelet count is outside of the 2-week window.

Subjects will receive a starting dose of 20 mg avatrombopag once daily and will be allowed to change their dose and dosing frequency (maximum dose 40 mg daily, minimum dose 20 mg once weekly) in accordance with their individual platelet responses. The overall goal of any dose modification will be to maintain the platelet count  $\geq 50 \times 10^9/L$  and  $< 200 \times 10^9/L$ , and to decrease the need for concomitant ITP medications.

The study will consist of 3 phases: Pre-enrollment, Primary Investigation (Core Phase), and Extension. The Pre-enrollment Phase will have 1 Screening Period (up to 4 weeks). The Primary Investigation Phase (Core Phase) will have 4 periods: Baseline (1 day), Titration (6 weeks), Concomitant ITP Medication Reduction (12 weeks), and Maintenance (8 weeks including the Endof-Treatment [EOT] Visit). Subjects will have weekly or bi-weekly visits during the 26-week Primary Investigation Phase (Core Phase) to collect the required platelet count data, bleeding events, and other AEs. All subjects who complete the Primary Investigation Phase (Core Phase) can continue to receive avatrombopag in the Extension Phase until market authorization in Japan. Safety and efficacy data will be collected monthly in the Extension Phase. Dose-tapering and Follow-up at the end of the Core Phase are required only for those subjects not continuing into the Extension Phase.

The total study duration of the Pre-enrollment and Primary Investigation Phase will be up to 7 months. Subjects may continue in the Extension Phase until market authorization in Japan.

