# 10.2.2 Analysis of Efficacy

## 10.2.2.1 Primary Investigation Phase (Core Phase) Efficacy Analyses

The primary efficacy variable, the cumulative number of weeks of platelet response, and key secondary efficacy variable, response rate at Day 8, will be determined in the FAS. Analyses in the PPS will be used as supportive evidence. All analyses of platelet counts will be based on local laboratory results.

The pre-defined hurdle for the primary efficacy endpoint is set such that the lower limit of the 95% confidence interval (CI) of the mean number of cumulative weeks of platelet response  $\geq 50 \times 10^9 / L$  will need to be  $\geq 8.02$  weeks.

Descriptive statistics will be generated to summarize effectiveness endpoints.

Effectiveness endpoints will be summarized as follows:

- Continuous variables will be summarized by number, mean, median, maximum, and minimum, as appropriate.
- Categorical variables will be summarized by number and percentage, as appropriate.

Additional analyses will be performed using appropriate statistical methodologies as deemed appropriate.

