8.3 Analysis Methods

8.3.1 Descriptive Statistics

Descriptive statistics:

| | |
|--------------------------------|--|
| Continuous data except for PK | PK concentration data |
| The number of subjects (N) | The number of subjects (N) |
| Arithmetic Mean | Arithmetic Mean |
| Standard Deviation (SD) | Standard Deviation (SD) |
| Median | Median |
| Minimum and Maximum | Minimum and Maximum |
| First quartile, Third quartile | - |
| - | The number and % of BLQ |
| | Coefficient of variation (CV%) for arithmetic mean |
| - | Geometric Mean |
| - | 95% confidence interval (CI) of geometric mean |
| - | Geometric CV% |

CV%, Geometric mean, 95% CI of geometric mean, and Geometric CV% are calculated using the following formula:

CV(%) = (standard deviation) / (arithmetic mean) × 100

$$\text{Geometric mean} = \exp \left[\frac{\sum_{i=1}^n \log X_i}{n} \right] = \sqrt[n]{\prod_{i=1}^n X_i}$$

95% CI of geometric mean = $\exp(\mu \pm 1.96 \cdot s/\sqrt{n})$

μ : mean on the natural logarithm scale

s: standard error on the natural logarithm scale

$$\text{Geometric CV(%) = } \sqrt{\exp(s^2) - 1} \times 100$$

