11.1 Primary Efficacy Endpoint

11.1.1 Cumulative Number of Weeks of Platelet Response

Population: Full Analysis Set, Per Protocol Set

Target Phases: Core Phase

Analysis items:

- The cumulative number of weeks in which the platelet count is $\geq 50 \times 10^9/L$ during 26 weeks of treatment in the absence of rescue therapy for each subject

Contents:

- Descriptive statistics and 95% CI of mean of the cumulative number of weeks of platelet response during 26 weeks of treatment in the absence of rescue therapy is calculated.

Definitions:

- Platelet response: platelet count of $\geq 50 \times 10^9/L$

- Cumulative number of weeks of platelet response during 26 weeks of treatment in the absence of rescue therapy is calculated by the formula: (sum of platelet response duration)/7= sum of (last day platelet response - the first day platelet response +1)/7.
- All scheduled and unscheduled visits will be used. If the subject missed a visit, the visit date will be imputed based on analysis target date.
- Platelet response will be defined with consideration referring the handling of data as described in 3 cases below:
 - 1. Subjects who have missing platelet assessments at any scheduled visit of interest will be considered as non-responders at that time point.
 - 2. Subjects who use rescue therapy at any time during the 26-week treatment period will be considered as non-responders for all subsequent days after rescue therapy start date.
 - 3. Subjects who discontinue the study or who are lost to follow-up before 26 weeks will have all subsequent unobserved scheduled platelet assessments at the scheduled time points as having “missing” platelet values.

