11.1.2 Cumulative Number of Weeks of Platelet Response by Subgroups

Population: Full Analysis Set, Per Protocol Set, Safety Set

Target Phases: Core Phase

Analysis items: - The cumulative number of weeks in which the platelet count is $\geq 50 \times 10^9/L$ during 26 weeks of treatment in the absence of rescue therapy

Contents: - Conduct a subgroup analysis for “[11.1.1 Cumulative Number of Weeks of Platelet Response](#)”. Planned subgroups are defined below:

- Sex (Male, Female)
- Age (<65 yrs, ≥ 65 yrs)
- Baseline platelet count ($\leq 15 \times 10^9/L$, $> 15 \times 10^9/L$)
- Use of concomitant ITP medications (Yes, No)
- Splenectomy status (Yes, No)
- Baseline creatinine clearance (30 \leq - <60 mL/min, 60 \leq - <90 mL/min, ≥ 90 mL/min, Missing (if any))

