Appendix 1: Sample Code

- Confidence Intervals for proportions

```
proc freq data=data;  
  tables targvar /out=cnt binomial alpha=0.05;  
  exact binomial;  
  ods output binomial= binomial;  
run;
```

Exact CI should be used.

- Confidence Intervals for mean

```
proc ttest data=data alpha=0.05;  
  class param;  
  var Height;  
run;
```

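### The 19 subjects said to be needed to clear the 8.02-week hurdle give only about an even chance of clearing it under the plan's own assumptions

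*Protocol*

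**What the plan says.** The success rule is in Protocol 10.2.2.1 and is repeated in the synopsis: the lower 95% confidence limit for the mean number of cumulative response weeks has to be 8.02 or more. The study is described as confirmatory (Protocol 1.5, SAP 4.1), and no other success criterion is stated.

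Protocol 10.2.5 takes 8.02 from the lower limit reported for an eltrombopag extension study. It assumes a mean of 12.0 weeks and an SD of 8.75, and concludes that "a sample size of 19 subjects would be required to meet this primary efficacy endpoint hurdle". SAP 6 repeats this. The synopsis puts it more firmly: "a sample size of 19 subjects is required to meet the primary efficacy endpoint hurdle". None of the three gives a formula, a power or a probability of success.

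On enrolment, Protocol 4.1 says "Approximately 19 subjects who meet all the eligibility requirements will be enrolled", while SAP 4.2 makes 19 a minimum.

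On the analysis, SAP 11.1.1 asks for "Descriptive statistics and 95% CI of mean of the cumulative number of weeks of platelet response" without naming the type of interval or mentioning 8.02. SAP Appendix 1, under its entry for confidence intervals of a mean, gives "proc ttest data=data alpha=0.05", which produces a t interval.

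**The concern.** The wording ties 19 to passing a pass/fail rule, so a reader will take it that 19 subjects suffice if the drug performs as assumed. A size at which the limit just touches the hurdle when the data equal the assumptions is a different thing from a size that makes success likely. Observed means fall below the assumed mean about half the time, so a calculation without a power term leaves the chance of success near one half. If the analysis then uses a wider interval than the calculation did, even the touching condition fails.

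At stake is the only success criterion of the study. Those who approve, fund or later interpret it would not know that a miss is about as likely as a pass when the drug works exactly as planned. A miss could then be misread as evidence against the drug in Japanese patients.

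**Working it through.** **Inputs.** Mean 12.0, SD 8.75, hurdle 8.02 and n = 19, all from Protocol 10.2.5 and SAP 6. The 95% interval is taken as two-sided, with 2.5% in the lower tail. The t method comes from SAP Appendix 1.

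Distance to the hurdle: 12.0 − 8.02 = 3.98. Standard error at n = 19: 8.75/√19 = 2.0074.

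**1. Reproducing 19.** Set the normal-quantile lower limit equal to the hurdle and solve for n:

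n = (1.96 × 8.75/3.98)² = 18.57, rounded up to 19.

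The limit is 7.96 at n = 18 and 12.0 − 1.96 × 2.0074 = 8.07 at n = 19. This matches the plan's figure exactly and contains no power term. That it is the origin of 19 is an inference, because the documents show no formula.

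**2. Which interval the SAP points to.** SAP 8.3.1, in its column "Continuous data except for PK", lists no confidence interval for the arithmetic mean. Only SAP 11.1.1 and its subgroup repeat, 11.1.2, call for one. The only code for such an interval is the t procedure in Appendix 1. The t interval is therefore the likely method.

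**3. Lower limit with t.** t(0.975, 18) = 2.1009, so the limit is 12.0 − 2.1009 × 2.0074 = 7.78. Shortfall: 8.02 − 7.78 = 0.24 weeks.

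**4. Chance of meeting the hurdle.** The limit reaches 8.02 when (observed mean − 8.02)/(standard error) is at least the critical value. The noncentrality is 3.98/2.0074 = 1.983.

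- t interval, normal data: probability that a noncentral t (18 df, noncentrality 1.983) is at least 2.1009 = 46.7%. Simulation of normal trials agrees.
- z interval, SD known: Φ(1.983 − 1.96) = 50.9%. Using the sample SD with 1.96 gives about 52% by simulation.

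**5. What the t interval needs at n = 19.** At SD 8.75, an observed mean of at least 8.02 + 2.1009 × 2.0074 = 12.24. At mean 12.0, an observed SD of at most 3.98 × √19/2.1009 = 8.26. Both are better than the planning assumptions.

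**6. Sensitivity to n.** This matters because enrolment is approximate in one document and a minimum in the other.

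| n | t limit | chance, t | z limit | chance, z |
|---|---|---|---|---|
| 18 | 7.65 | 44.5% | 7.96 | 49% |
| 19 | 7.78 | 46.7% | 8.07 | 51% |
| 20 | 7.90 | 48.8% | 8.17 | 53% |
| 21 | 8.017 | 51.0% | 8.26 | 55% |
| 22 | 8.12 | 53.0% | 8.34 | 57% |

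The t limit first clears 8.02 at n = 22, and even there the chance is only 53%.

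**7. Sensitivity to shape.** The endpoint is bounded by 0 and 26 weeks and the documents give no distribution. Assuming a beta distribution scaled to 0–26 weeks with the same mean and SD (parameters 0.551 and 0.643), simulation with the t interval at n = 19 gives about 44%.

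**The case against.** The best reply is that 19 is not an arithmetic slip. With a normal-quantile interval it is the smallest size at which the assumed mean and SD put the limit above 8.02 (7.96 at 18, 8.07 at 19). On that reading the text is a correct statement about precision and never promised power.

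The method is also not nailed down. The Appendix 1 code is a generic template with height as its variable, SAP 11.1.1 does not refer to it, and the one interval formula that SAP 8.3.1 writes out uses 1.96.

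Further, low power does not raise the risk of passing wrongly, and rewriting a rationale changes no operating characteristic. The SAP cites dictionaries dated September 2023, which suggests that data were already accruing and that a protocol amendment would come late.

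Some of this stands. The 7.78 is conditional on the t interval, and the sponsor should confirm the method. The fix discloses the chance of success and does not improve it. The main conclusion survives, though. The 1.96 formula is for geometric means of drug concentrations, whereas Appendix 1 is expressly about the interval for a mean. Above all, the choice of method moves the chance only between about 47% and 51%. On either reading it is close to one half and is not disclosed.

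**Conclusion.** The concern holds. Under the plan's own mean and SD, 19 subjects give about a 47% chance of meeting the hurdle with the t interval and about 51% with a normal-quantile interval. With t, the limit computed at the assumed values is 7.78, which is 0.24 weeks short.

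The conclusion rests on the two-sided reading of the 95% interval and, for the 46.7% and 50.9% figures, on normal data. Over the two shapes tried with the t interval, the range is 44% to 47%. Enrolling one subject fewer or one more does not alter it.

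The statement concerns the sole success criterion and appears in three places, so it must be corrected.

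**What to change.** In Protocol 10.2.5, the synopsis and SAP 6, replace the sentence on the required size with, for example:

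> At n = 19, with mean 12.0 and SD 8.75, the t-based lower 95% limit is 7.78 weeks. The probability that the lower limit is at least 8.02 is about 47% under normality (about 51% by normal approximation).

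The sponsor should add the actual basis on which 19 was chosen.

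In SAP 11.1.1, refer to Appendix 1 and state that the two-sided t-based 95% interval of the mean in the Full Analysis Set (the set fixed by Protocol 10.2.2.1) is compared, unrounded, with 8.02. Before this is written in, the sponsor should confirm that t is intended. If a normal-quantile interval was meant, naming t raises the observed mean needed at SD 8.75 from 8.02 + 1.96 × 2.0074 = 11.95 to 12.24 weeks.

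For scale only: the documents set no power target, but under the same assumptions and a t interval 80% power would need 40 subjects and 90% would need 53.

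Cost: no added patients and no change to the hurdle or the estimate, but a less favourable planning statement. The protocol text needs an amendment through the review and approval described in Protocol 12.3. The SAP text can be changed until the SAP is locked, which SAP 2 places before the Core Phase database lock.

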#### 11 DATA MANAGEMENT AND RECORD KEEPING

# 11.1 Data Management

# 11.1.1 Data Handling

Data will be recorded at the site on eCRFs and reviewed by the clinical research associate (CRA) on an ongoing basis and during monitoring visits. The CRAs will verify data recorded in the electronic data capture (EDC) system with source documents. All corrections or changes made to any study data must be appropriately tracked in an audit trail in the EDC system. An eCRF will be considered complete when all missing, incorrect, and/or inconsistent data has been accounted for and reconciliation between other databases (e.g., safety) is complete.

## 11.1.2 Computer Systems

Data will be processed using a validated computer system conforming to regulatory requirements.

# 11.1.3 Data Entry

Data must be recorded using the EDC system as the study is in progress. All site personnel must log into the system using their secure username and password in order to enter, review, or correct study data. These procedures must comply with relevant national and international regulations. All passwords will be strictly confidential.

# 11.1.4 Medical Information Coding

For medical information, the thesauri listed below will be used:

- Medical Dictionary for Regulatory Activities (MedDRA) for medical history and adverse events
- World Health Organization Drug Dictionary (WHODrug) for concomitant medications.

#### 11.1.5 Data Validation

Validation checks programmed within the EDC system, as well as supplemental validation performed via review of the downloaded data, will be applied to the data in order to ensure accurate, consistent, and reliable data. Data identified as erroneous, or data that are missing, will be referred to the investigative site for resolution through data queries.

The eCRFs must be reviewed and electronically signed by the Investigator.

# 11.2 Record Keeping

Records of subjects, source documents, monitoring visit logs, eCRFs, inventory of study drug, regulatory documents, and other Sponsor correspondence pertaining to the study must be kept in the appropriate study files at the site. Source data are defined as all information in original records and certified copies of original records of clinical findings, observations, or other activities in a clinical study necessary for the evaluation and reconstruction of the clinical study. Source data are contained in source documents (original records or certified copies). These records will be retained in a secure file for the period as set forth in the clinical trial agreement. Prior to transfer or destruction of these records, the Sponsor must be notified in writing and be given the opportunity to further store such records.

# 12 INVESTIGATOR REQUIREMENTS AND QUALITY CONTROL

# 12.1 Ethical Conduct of the Study

This study will be conducted in compliance with the protocol and all regulatory requirements, in accordance with Good Clinical Practice (GCP), including International Council for Harmonisation (ICH) guidelines, and in general conformity with the most recent version of the Declaration of Helsinki. The sponsor's Quality Assurance personnel or designee may verify adherence to these practices and procedures through audit and inspection.

# 12.2 Institutional Review Board/Independent Ethics Committee

The IRB/IEC will review all appropriate study documentation in order to safeguard the rights, safety, and well-being of subjects. The study will only be conducted at sites where IRB/IEC approval has been obtained. The protocol, Investigator's Brochure, ICF, advertisements (if applicable), written information given to the subjects, safety updates, annual progress reports, and any revisions to these documents will be provided to the IRB/IEC by the Head of Medical Institution.

The Investigator is obligated to keep the IRB/IEC informed of any unanticipated problems. This may include notification to the IRB/IEC of SUSARs.

Federal regulations and ICH require that approval be obtained from an IRB/IEC prior to participation of subjects in research studies. Prior to study onset, the protocol, any protocol amendments, ICFs, advertisements to be used for subject recruitment, and any other written information regarding this study to be provided to a subject or subject's legal guardian must be approved by the IRB/IEC.

No drug will be released to the site for dosing until written IRB/IEC authorization has been received by the Sponsor.

It is the responsibility of the Sponsor or their designee to obtain the approval of the responsible ethics committees according to the national regulations.

The study will only start in the respective sites once the respective committee's written approval has been given.

#### 12.3 Protocol Amendments

Any amendments to the study protocol will be communicated to the Investigators by the Sponsor or designee. All protocol amendments will undergo the same review and approval process as the original protocol. A protocol amendment may be implemented after it has been approved by the IRB/IEC and submitted to/approved by regulatory authorities as required unless immediate implementation is necessary for subject safety. Urgent implementation of an amendment due to safety concerns must be documented and reported to the IRB/IEC within 5 working days.

## 12.4 Informed Consent

The ICF and any changes to the ICF made during the course of the study must be agreed to by the Sponsor or designee and the IRB/IEC prior to its use and must be in compliance with all ICH GCP, local regulatory requirements, and legal requirements.

The Investigator must ensure that each study subject is fully informed about the nature and objectives of the study and possible risks associated with participation and must ensure that the subject has been informed of his/her rights to privacy. The Investigator will obtain written informed consent from each subject before any study-specific activity is performed and should document in the source documentation that consent was obtained prior to enrollment in the study. The original signed ICF must be maintained by the Investigator and is subject to inspection by a representative of the Sponsor, their representatives, auditors, the IRB/IEC, and/or regulatory agencies. A copy of the signed ICF will be given to the subject.

